With the Research Methods Core, Drs. [name] and [name] will standardize data between clinics to the extent possible and determine the best approach to create a pooled dataset. Baseline EHR data collection will commence immediately after randomization. Follow-up data collection will be conducted after the 1-year study period is complete.

Clinic level - patient volume (number of active adult patients aged 18+ years during the 12-month study period, total number of primary care clinic visits), number of PCPs, and number of patients at risk of ADRD (active patients aged 55+ with no prior ADRD diagnosis), total number of visits, visits by PCP and provider type, and aggregate counts of new diagnoses (MCI, ADRD, other dementia) based on the ICD-10 codes for these diagnoses. Total patient volumes for patients aged 55-64 and 65+ will be used for clinic-based calculations of the cumulative incidence and prevalence of MCI, ADRD, and dementia.

Patient Level - The goal of this analysis is to determine whether patients with diagnosed ADRD received healthcare consistent with current quality of care standards. Eligible clinic patients are active clinic patient with prevalent ADRD as of the first day of the 12-month baseline [or follow-up] surveillance interval, age 55 or older at the start of the surveillance interval, at least one primary care clinic visit during the 12-month baseline [or follow-up] surveillance interval.

Data extraction domains

- 1. Demographics age, sex, marital and employment status/income, education, language(s) spoken, health insurance
- 2. Comorbidities hypertension, type 2 diabetes, hyperlipidemia, obesity, heart disease, stroke, sleep apnea, and smoking
- 3. Neuroimaging orders

- 4. New prescriptions for potentially beneficial drugs for ADRD symptoms (e.g., cholinesterase inhibitors, N-methyl-D-aspartate antagonists, antidepressants, and antipsychotics) in clinics that track such information in their EHR.
- 5. ADRD quality of care measures, as reported during the Clinic Profile Interview with clinic directors or administrative leadership.
- 6. Quality of care outcomes will be based on existing quality indicators. These comprise 5 domains of care for patients diagnosed with dementia: annual cognitive assessments, annual evaluation of functional status, annual behavioral and psychiatric screening, advance care directives, pharmacological treatment changes.

Manual Medical Chart review

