We will use hierarchical regression models with a random intercept for clinic; model specification will reflect that all PCPs within a clinic share the same intervention status. Linear hierarchical models will be used for continuous outcomes and logistic hierarchical models for binary outcomes. The intervention effect will be interpreted as the fixed effect for the INTACT × time (baseline vs. follow up) interaction. We will analyze PCP-specific outcomes using 2 approaches: a within-PCP change analysis and a within-clinic change analysis. For the analysis of within-PCP change, we will restrict the dataset to PCPs who participate in both baseline and follow-up data collection. These models will specify longitudinal data with 2 time points per PCP. Here, the INTACT × time interaction term will be interpreted as the intervention's effect on individual PCPs over time. For the analysis of within-clinic change, the dataset will include all PCPs who participate in data collection at baseline or follow-up regardless of whether they participate in both. The INTACT × time interaction term will be interpreted as the intervention's effect on the clinic environment. Primary analysis will not adjust for covariates. Secondary analyses will adjust for the same set of clinic covariates selected a priori, as above, and for clinic- and PCP-level covariates observed to be unbalanced between groups by chance alone.

Clinic Outcomes (Aim 3)

Incidence rates of new MCI, ADRD, and other dementia diagnoses will be estimated at each clinic for the 12-month intervention period using HER data. All patients aged 55+ who are at risk of the outcome during the study will be included. Poisson regression models will be used to estimate the effect of the intervention on changes in diagnosis rates for MCI, ADRD, and other dementia between intervention and control arms. Poisson models will include number of person years as an offset term. We will be parsimonious in our choice of adjustment variables, but will consider patient volume, state, and type of

facility if an imbalance is apparent after randomization. If we find evidence of an imbalance in covariates between study arms, we will adjust for those variables in the regression analysis.

Patient Outcomes (Aim 3)

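### Cumulative incidence of new diagnoses is divided by total patient volume, which includes people already diagnosed, and the listed at-risk count does not fit MCI

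*Combined protocol and SAP*

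**What the plan says.** Two sections describe the denominator for new diagnoses.

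- **EHR data Extraction, clinic level.** The numerator is "aggregate counts of new diagnoses (MCI, ADRD, other dementia) based on the ICD-10 codes for these diagnoses". The listed denominators are a volume, "number of active adult patients aged 18+ years during the 12-month study period", and an at-risk head count, "number of patients at risk of ADRD (active patients aged 55+ with no prior ADRD diagnosis". The paragraph then closes with the rule: "Total patient volumes for patients aged 55-64 and 65+ will be used for clinic-based calculations of the cumulative incidence and prevalence" of the three conditions. One denominator therefore serves both measures.
- **Clinic Outcomes (Aim 3).** Incidence rates "will be estimated at each clinic for the 12-month intervention period", and the population is restricted: "All patients aged 55+ who are at risk of the outcome during the study will be included". For the model, "Poisson models will include number of person years as an offset term".

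The clinic-level list contains no person-time and no entry, exit or diagnosis dates. Neither section says how person-years are obtained from the counts, or how the cumulative incidence in one section relates to the incidence rate in the other.

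**The concern.** A cumulative incidence needs a denominator of people who could still become new cases. Total volume in an age band also contains everyone who already carries the diagnosis. The extraction section therefore states a rule that gives too low an answer and disagrees with the analysis section about who is counted.

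The at-risk count that could replace it is itself incomplete. It removes patients with earlier ADRD only, yet MCI, ADRD and other dementia are analysed as separate outcomes. A patient with recorded MCI and no ADRD stays in the count although that patient cannot have a first MCI diagnosis.

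New diagnoses are the clinic-level outcome named in Aim 3, so the reported incidence figures are at stake. The data are extracted as aggregates, so a denominator left out of the query cannot be rebuilt later without running the query again.

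**Working it through.** The plan states no incidence, event count, rate ratio or power for new diagnoses, so there is no figure to reproduce. Prevalence, incidence and turnover below are assumptions shown as ranges. The 12-month window and the 28 clinics (14 per arm) come from the protocol.

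**1. Total volume as the incidence denominator.** Let D be new diagnoses, N total volume in the band, and p the share already diagnosed at the start.

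- As written: D / N.
- Among those at risk: D / [N(1 - p)].
- Ratio of the first to the second: 1 - p.

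| Assumed p | Factor on cumulative incidence |
|---|---|
| 2% | 0.98 |
| 5% | 0.95 |
| 10% | 0.90 |
| 15% | 0.85 |
| 20% | 0.80 |

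For prevalence the same denominator gives pN / N = p, which is correct.

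**2. The listed at-risk count, by outcome.** If a share m of that count already has the outcome in question, incidence on it is multiplied by (1 - m).

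- ADRD: m = 0 by definition, so the count fits.
- MCI: m is the share with earlier MCI and no ADRD. If m were 5-15% (assumed), the factor would be 0.95-0.85.
- Other dementia: the result depends on whether the ADRD definition covers it, which the documents do not say.

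**3. Whether the rate model has an exposure.** Every clinic has the same 12-month window, so at-risk count x 1 year is available. If cases and leavers each contribute half a year on average, true person-time per person is 1 - i/2 - f/2, where i is incidence and f is turnover.

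- i = 1-5%, f = 0: 0.995 to 0.975 years, so the rate is understated by 0.5-2.5%.
- i = 1-5%, f = 20%: 0.895 to 0.875 years, so the rate is understated by 10.5-12.5%.
- Effect on the arm ratio from turnover: (1 - f_I/2) / (1 - f_C/2), with I for intervention and C for control. This is 1 when turnover is equal, and 0.95 / 0.90 = 1.056 at 10% (intervention) against 20% (control).

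**4. Illustrative fit.** One data set of 28 clinics was simulated with 10% prevalence and 0.93 person-years per at-risk patient in both arms. A Poisson model was fitted with the log of each denominator as offset.

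| Offset | Converged | Baseline rate | Rate ratio |
|---|---|---|---|
| Person-years | yes | 0.0306 | 1.373 |
| At-risk count | yes | 0.0285 | 1.373 |
| Total volume | yes | 0.0256 | 1.372 |

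The baseline rate moves and the ratio does not. That follows from the set-up: when the denominators are proportional in both arms, the difference goes into the intercept. The fit shows that the model runs. It does not show that the ratio is safe when prevalence or turnover differs by arm.

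**The case against.** The best defence is that the extraction sentence is descriptive and concerns per-clinic figures. The comparison of arms is specified in Clinic Outcomes (Aim 3), which already restricts to patients at risk. An at-risk count is in the extraction list, so an analyst would probably use it. The list is also a summary, since the clinic profile interview is meant to tailor extraction at each site.

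Much of this stands, and it rules out three stronger readings that a reader might infer.

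- *That the Poisson model cannot be fitted because person-time is not extracted.* The at-risk count and the fixed window give a usable approximate exposure. What is missing is a statement of that derivation.
- *That the arm comparison is biased.* With total volume in the model, the ratio would be multiplied by (1 - p_I) / (1 - p_C): 0.88 / 0.92 = 0.957 at 12% against 8%, and 0.85 / 0.95 = 0.895 at 15% against 5%. But the extraction sentence is nowhere said to supply the model's denominator, and the analysis section specifies a different one. Those factors do not apply to the planned treatment effect.
- *That person-years would be entered without taking logs.* The phrase is ordinary shorthand for an exposure term. At most it is a point of wording.

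The defence does not remove the stated rule. The text ties total volume to cumulative incidence, and no exclusion is given. Nor does it answer the MCI mismatch, because the at-risk count it relies on is the one defined by ADRD alone.

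**Conclusion.** The point holds in a limited form. The denominator stated for cumulative incidence is wrong and contradicts the at-risk population in the analysis section. Taken literally, it understates cumulative incidence by exactly the diagnosed prevalence: 5-15% at an assumed prevalence of 5-15%, and 2-20% over the wider range tabulated. Separately, the listed at-risk count is not the right one for MCI, by an amount that the documents do not allow to be estimated.

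The harm is to the reported incidence figures. Bias in the planned rate ratio is not shown. It could arise from the person-years approximation only if turnover differed between arms, and nothing in the documents indicates that it will.

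**What to change.** Three changes, made before the EHR query is finalised:

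1. In EHR data Extraction, keep total volume in the two age bands for prevalence only.
2. For every incidence measure, extract the number of active patients aged 55+, by the 55-64 and 65+ bands, who do not have that specific diagnosis on the first day of the 12-month interval. Do this separately for MCI, ADRD and other dementia. State whether an earlier dementia code also removes a patient from the MCI count.
3. In Clinic Outcomes (Aim 3), state that person-years are formed from these same counts, as at-risk count x 1 year or as dated person-time where the EHR supplies it, and enter the model as a log offset.

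The cost is a few more aggregate counts per clinic and interval, plus some sentences in the plan. The downside is that count x 1 year ignores turnover where dates are not available, so that limitation should be reported. Full patient-level person-time across 28 clinics' records is not needed to correct the error and is not shown to be cheap.

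### The clinic diagnosis-rate model targets changes in rates but defines the rate for the intervention year only and names no baseline term

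*Combined protocol and SAP*

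**What the plan says.** Clinic Outcomes (Aim 3) states that the incidence rates "will be estimated at each clinic for the 12-month intervention period". It then gives the purpose of the Poisson models: to "estimate the effect of the intervention on changes in diagnosis rates for MCI, ADRD, and other dementia between intervention and control arms". On the content of the model it says only this:

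- "Poisson models will include number of person years as an offset term".
- Covariates are to be few; the candidates named are clinic size in patients, state and facility type, and they come into play only when the arms look unbalanced.
- "If we find evidence of an imbalance in covariates between study arms, we will adjust for those variables in the regression analysis".

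Under EHR data Extraction, "Baseline EHR data collection will commence immediately after randomization", and follow-up extraction comes after the study year. The clinic-level list there includes "aggregate counts of new diagnoses (MCI, ADRD, other dementia) based on the ICD-10 codes for these diagnoses". A 12-month baseline interval is spelled out only in the patient-level paragraph. The clinic-level item on patient volume refers to the 12-month study period.

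For PCP outcomes, the intervention effect is the INTACT × time interaction (baseline versus follow-up). Patient Outcomes (Aim 3) adopts the same approach by reference. The exploratory analysis of sex adjusts for the baseline value.

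**The concern.** A change needs two time points, and the clinic paragraph defines the rate for one. None of the named terms turns a follow-up comparison into a comparison of changes, so two analysts could fit different models from the same text: one on the intervention year alone, one with a baseline contrast. The clinic level is the only one of the three outcome levels without a baseline term.

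Clinics probably differ in coding habits, case mix and readiness to diagnose, and some of that persists from year to year. With 28 clinics, persistent differences add noise to the arm comparison and can leave the arms unequal by chance. The Randomization section says clinic-level EHR data cannot be completed before randomization, so the extracted baseline rate cannot be used to balance the arms. The model is where it can be taken into account. The imbalance-triggered adjustment is a weak substitute: the baseline rate is not among the named candidates, and whether to adjust would depend on the data.

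**Working it through.** **The plan's own figures.** The Power section covers only PCP and patient outcomes. With 14 clinics per arm, m people per clinic and design effect DE = 1 + (m − 1) × ICC, the detectable effect at 80% power and two-sided alpha 0.05 is d = (1.960 + 0.842) × √(2·DE/(14m)).

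- PCP, m = 5: DE is 1.04 at ICC 0.01 and 1.20 at ICC 0.05, so d is 0.483 and 0.519. The plan says 0.5.
- Patients, m = 50: DE is 1.49 and 3.45, so d is 0.183 and 0.278. The plan says 0.2 to 0.3.

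These reproduce. The diagnosis-rate outcome has no power figure.

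**Inputs for the diagnosis rate.** From the documents: 28 clinics, 14 per arm. Assumed, because the documents give none: μ = 2 to 10 new diagnoses per clinic-year, between-clinic coefficient of variation CV = 0.3 to 0.8, and correlation c = 0.8 between a clinic's true log rates in successive years.

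**Chance imbalance.** The SD of the between-arm difference in mean log clinic rate is √(2·ln(1 + CV²)/14), which is 0.11, 0.18 and 0.27 for CV 0.3, 0.5 and 0.8.

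**Standard error of the log rate ratio.**

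- Per-clinic variance: v = 1/μ + ln(1 + CV²)
- Follow-up year only: SE = √(2v/14)
- Observed year-to-year correlation: r = c·ln(1 + CV²)/v
- Baseline-adjusted: SE × √(1 − r²)
- Arm × period: SE × √(2(1 − r))

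Example for μ = 5, CV = 0.5: ln(1.25) = 0.223; v = 0.200 + 0.223 = 0.423; SE = √(0.846/14) = 0.246; r = 0.8 × 0.223/0.423 = 0.42. Adjusted SE = 0.246 × √(1 − 0.42²) = 0.223. Arm × period SE = 0.246 × √(2 × 0.58) = 0.264 (unrounded r).

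The detectable rate ratio at 80% power is exp(2.802 × SE):

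| μ | CV | r | Follow-up only | Baseline-adjusted | Arm × period | SE reduction from adjustment |
|---|---|---|---|---|---|---|
| 2 | 0.3 | 0.12 | 2.25 | 2.24 | 2.94 | about 1% |
| 5 | 0.5 | 0.42 | 1.99 | 1.87 | 2.10 | about 9% |
| 10 | 0.5 | 0.55 | 1.83 | 1.65 | 1.77 | about 17% |
| 10 | 0.8 | 0.67 | 2.26 | 1.84 | 1.95 | about 25% |

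Arm × period is less precise than the follow-up comparison whenever 2(1 − r) > 1, that is, r < 0.5.

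**Does the reported interval show the gain?** In a plain Poisson model the standard error comes from the counts alone. Simulating 28 clinics with c = 0.8, with and without log(count + 0.5) from the baseline year as a covariate, gave:

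| μ | CV | True SD of estimate, without → with | Mean model SE, without → with | Type I error with covariate |
|---|---|---|---|---|
| 5 | 0.5 | 0.258 → 0.242 | 0.171 → 0.175 | 0.15 |
| 10 | 0.5 | 0.225 → 0.190 | 0.121 → 0.123 | 0.20 |
| 10 | 0.8 | 0.315 → 0.247 | 0.122 → 0.125 | 0.32 |

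Over the full assumed range the true SD changed by about +1% to −23%. The estimate becomes more precise, but the plain Poisson interval does not show it and stays too narrow.

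**The case against.** The strongest reply is that a follow-up comparison of randomized arms is unbiased, so apart from a loose word this is a preference about precision. The first part is right: a reader might infer a biased result, and nothing in the documents supports that. What remains is the mismatch with the stated target and the lost precision.

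A second reply is that the paragraph is not a full model specification. It does not list even the arm indicator, and the word for change may signal that a baseline contrast was intended. That also stands: the text is under-specified, and it does not show a decision to exclude the baseline. But no stated term delivers the contrast, so the wording has to be settled.

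Third, extraction of prior-year incident counts with person-time at clinic level is implied by the general statements on baseline collection, not written out. The eligibility rule against changing EHR systems looks only at the coming year, so the prior-year query may be harder in some clinics. This limits how cheap the change can be assumed to be, and is a reason to specify the query.

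Fourth, a reader might apply √(1 − r²) with r of 0.5, 0.7 or 0.8 and expect intervals 13%, 29% or 40% narrower. That does not carry over. Count noise pulls the observed correlation down (0.12 to 0.67 in the cases above), and a plain Poisson interval does not narrow at all.

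**Conclusion.** The point holds as a gap between target and model, with a moderate and uncertain cost in precision. The plan promises an effect on changes, defines the rate for one year and names no baseline term. Always adjusting for the clinic's baseline rate would lower the true standard error by roughly 0% to 25% under the assumed values (2 to 10 diagnoses per clinic-year, CV 0.3 to 0.8, clinic correlation 0.8). At about 2 diagnoses per clinic and low CV the gain is negligible. These assumptions carry the size; the mismatch itself rests on the text alone.

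A reader might also take this to undermine the main Aim 3 result. The documents do not rank the clinic outcome above the patient outcomes, and within Aim 3 they call only patient outcomes primary.

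**What to change.** In Clinic Outcomes (Aim 3) and EHR data Extraction:

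1. State that new-diagnosis counts and at-risk person-years are extracted for the 12-month baseline year by the same EHR query as follow-up.
2. Include each clinic's log baseline rate, for example log((count + 0.5)/person-years), as a prespecified covariate in every diagnosis-rate model, whether or not imbalance is seen. Describe the estimand as the between-arm rate ratio in the intervention year, adjusted for baseline rate.
3. Allow for between-clinic variation: a clinic random effect, a negative binomial model, or scaled or robust standard errors, with a small-sample correction. Without this the interval will not reflect the gain.
4. Prefer the covariate to an INTACT × time term, which loses precision against the follow-up comparison when the observed correlation is below 0.5.

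If baseline-year counts cannot be obtained, drop the reference to changes.

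Cost: SAP wording, one degree of freedom and one prior-year EHR query per clinic.

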Prior to starting data collection and delivering the INTACT intervention program, Drs. [name] and [name] will conduct a Clinic Profile Interview to learn about the clinic's set up, unique organizational and clinical workflow features, current protocol, and practices with ADRD, the clinic and local resources,

and their Al/AN patient population, The information will be used to tailor the implementation of the INTACT intervention at the PCP and clinic level, and EHR data extraction procedures.

Randomization

Randomization will occur at the clinic level after completion of the PCP baseline data collection. Clinicand patient-level data collection rely on EHR queries and manual chart review, and it is not logistically feasible to complete these before randomization. Clinics will be randomized in batches with at least 2 clinics per batch, to ensure simultaneous launch with at least one clinic in each study arm.

Note on immediate intervention arm engagement

For the 14 clinics randomized to the immediate intervention arm, clinic leadership will announce their participation in INTACT and will encourage all PCPs to participate in the programmatic elements for professional development and ADRD-related capacity-building. All PCPs employed at the clinic at any time during the 1-year study period are invited to engage with all aspects of the intervention, including those who are newly hired during the study period. For clinics in the immediate intervention arm, PCP participation in the study-specific data collection is not contingent on active engagement with the intervention; any PCP who meets eligibility criteria can complete the self-report questionnaires at baseline and follow-up.

Data collection

Data will be collected in three ways: self-report (PCP surveys and clinic profile data), EHR query (clinic and patient data), and manual chart review (patient data).

PCP Survey

Within each clinic, each participating PCP will complete a baseline and a 12-month follow-up survey. Outcomes will include basic demographics (sex, age, race), care confidence in providing dementia care to patients and their families and other PCP-level variables such as medical specialty, years of practice, tenure at the clinic.

EHR data Extraction

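### The new-diagnosis Poisson model pre-specifies no age term and leaves its form open; if it compares arms at follow-up only, chance differences in clinic age mix cost precision

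*Combined protocol and SAP*

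**What the plan says.** Under Clinic Outcomes (Aim 3) in the combined protocol and SAP, the population for the diagnosis model is a single group: "All patients aged 55+ who are at risk of the outcome during the study will be included". The exposure is handled by one statement: "Poisson models will include number of person years as an offset term". No age term appears. The adjustment variables named for consideration are patient volume, state and facility type. A further sentence commits to adjusting for covariates found to be imbalanced between arms.

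Under EHR data Extraction, the clinic-level list does split the population at 65, but for another purpose: "Total patient volumes for patients aged 55-64 and 65+ will be used for clinic-based calculations of the cumulative incidence and prevalence". The outcome is described as "aggregate counts of new diagnoses (MCI, ADRD, other dementia) based on the ICD-10 codes for these diagnoses", with no split by age.

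The form of the comparison can be read in two ways. The rates "will be estimated at each clinic for the 12-month intervention period", which suggests follow-up data only. Yet "Poisson regression models will be used to estimate the effect of the intervention on changes in diagnosis rates", which suggests a contrast with baseline, and baseline EHR data are collected.

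On allocation, the Randomization section says that "Clinics will be randomized in batches with at least 2 clinics per batch" and names no stratification factor. The note on intervention-arm engagement fixes the arm size: "For the 14 clinics randomized to the immediate intervention arm", out of 28.

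**The concern.** Age is a strong and foreseeable predictor of a new dementia diagnosis. The plan treats 65 as a useful cut when it describes incidence and prevalence, but does not carry the cut into the model that estimates the intervention effect. With 14 clinics per arm and no stratification on age mix, the arms can differ by chance in the share of patients aged 65+. In a comparison of follow-up rates with no age term, that difference becomes part of the estimated rate ratio and of the unexplained variation between clinics. At stake is the precision of the clinic-level outcome in Specific Aim 3. A plain Poisson model that ignores this extra variation would also have intervals that are somewhat too narrow.

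**Working it through.** **The plan's own figures.** The Power section gives no figure for the diagnosis rate. Its detectable effects for the other outcomes reproduce with 14 clinics per arm, m subjects per clinic, and two-sided alpha of 0.05 (sidedness is my assumption): n_eff = 14m / (1 + (m − 1) × ICC) and d = (1.960 + 0.842) × √(2 / n_eff).
- Providers, m = 5: n_eff = 67.3 (ICC 0.01) or 58.3 (ICC 0.05), so d = 0.483 to 0.519, against 0.5 stated.
- Patients, m = 50: n_eff = 469.8 or 202.9, so d = 0.183 to 0.278, against 0.2 to 0.3 stated.

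These agree to the stated rounding and do not bear on age mix.

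**Age mix in a follow-up-only model.** Let p be a clinic's share aged 65+ and R the ratio of the diagnosis rate at 65+ to that at 55-64. The pooled rate is proportional to 1 + (R − 1)p. With equal-sized clinics:
- SD of the between-arm difference in mean p = SD_p × √(2/14)
- SD of the age-mix part of log RR ≈ (R − 1) × SD_p × √(2/14) / (1 + (R − 1) × mean p)

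Assumed, because the documents give no values: mean p 0.45, SD_p 0.05 to 0.15, R 2 to 8. For SD_p 0.10 and R 5, this is 4 × 0.0378 / 2.8 = 0.054, a rate ratio of 1.055 at 1 SD and 1.11 at 1.96 SD. SD of log RR across the range:

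| SD_p | R = 2 | R = 3 | R = 5 | R = 8 |
|---|---|---|---|---|
| 0.05 | 0.013 | 0.020 | 0.027 | 0.032 |
| 0.10 | 0.026 | 0.040 | 0.054 | 0.064 |
| 0.15 | 0.039 | 0.060 | 0.081 | 0.096 |

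At 1 SD the rate ratio is therefore off by 1.3% to 10%.

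**Unequal clinic sizes.** With an assumed size CV of 0.6, these SDs grow by √(1 + 0.36) = 1.17: to 0.046 for R 3, SD_p 0.10, and to 0.11 for R 8, SD_p 0.15. Simulated allocations give 95% ranges of about 0.91 to 1.09 and 0.81 to 1.24 for those two cases, with the ratio off by more than 10% in 4% and 38% of allocations. At SD_p 0.05 and R 3 the range is only 0.96 to 1.05.

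**What an age term recovers.** Simulation with no intervention effect, assuming about 200 at-risk patients per clinic, 1% per year at 55-64, and no other variation between clinics. Entries are the SD of log RR, then the type I error of a plain Poisson test:

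| R, SD_p | Follow-up only, no age term | Share 65+ as covariate | Age-band rows | Arm × period |
|---|---|---|---|---|
| 3, 0.10 | 0.193, 5.8% | 0.193, 4.9% | 0.188, 5.2% | 0.263, 4.3% |
| 5, 0.10 | 0.161, 6.1% | 0.154, 5.0% | 0.150, 4.4% | 0.216, 4.9% |
| 5, 0.15 | 0.179, 9.3% | 0.157, 4.8% | 0.151, 4.6% | 0.215, 5.1% |

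Mean log RR was close to 0 for every model. In a noise-free check on one set of clinics with the share aged 65+ raised in one arm, the follow-up-only model gave an expected ratio of 1.045 and the arm × period model 1.000.

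**Other clinic variation.** Adding a clinic log-rate SD of 0.3, held constant over both years, raised type I error of the follow-up-only model to 11% to 20%. Age adjustment left it at 10% to 16%. The arm × period model stayed at 5% to 6%.

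**The case against.** The strongest reply is that the stated target is change in diagnosis rates. In a change model, a stable age mix cancels. Even if each clinic's share aged 65+ drifts by an assumed SD of 2 points between years, the 95% range with size CV 0.6 is 0.98 to 1.02 (R 3) to 0.97 to 1.03 (R 8). This stands, and it rules out an inference that a reader might draw: that differences in age mix necessarily pass into the rate ratio. It does not close the matter, because the clinic section names no arm × period term, baseline rate or clinic term. The PCP section does name its interaction with time, so the omission leaves the follow-up-only reading open.

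The second reply is the imbalance sentence, which is not limited to the three named variables and could bring age in. That is true, but it operates after randomisation, has no threshold and does not name age. It is a weak substitute for naming a predictor that is known in advance to be strong.

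Third, the size rests on assumed inputs. At the mild end (R 3, SD_p 0.10) the share covariate left the SD of log RR at 0.193, so the gain in precision there is negligible. This also stands.

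**Conclusion.** The point holds as a gap in specification with a modest and conditional cost. The model pools everyone aged 55+, pre-specifies no age term, and does not say whether it is a follow-up-only or a change comparison. Under the follow-up-only reading, chance age mix moves the rate ratio by about 1% to 10% at 1 SD with equal-sized clinics, and slightly more with unequal sizes. This rests on assumed values for age mix, its spread and the age-specific rate ratio.

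Two stronger readings are not supported. The first is that the result would be biased: allocation is random, so the expected log rate ratio is unaffected and the harm is chance error and lost precision. The second is that everything needed for a banded model is already being collected: the plan extracts volumes by band, but states neither new-diagnosis counts nor at-risk person-years by band.

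**What to change.** In Clinic Outcomes (Aim 3), make two statements.

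1. **Model form.** Say whether the primary model has an arm × period term or adjusts follow-up for the baseline rate. The arm × period form removes a stable age mix but carries the sampling noise of the baseline count: the SD of log RR was 0.215 against 0.151 for age-band rows in the R 5, SD_p 0.15 case without other clinic variation.

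2. **Age.** Pre-specify it in the primary model in one of two ways:
   - each clinic's share aged 65+, preferably from the baseline interval, formed from volumes already extracted. These are total volumes, so the share only approximates that of the at-risk population; or
   - two rows per clinic (55-64 and 65+), each with its own count and person-years, a fixed age-band term and a shared INTACT effect.

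The first option costs one model term and recovered most of the gain (SD 0.157 against 0.151 in the same case). The second also requires the EHR query to return new-diagnosis counts and at-risk person-years by band from every clinic. Neither adds patients or visits.

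Age adjustment does not replace a clinic-level or overdispersion term. In the follow-up-only simulations with other clinic variation, the lack of such a term had the larger effect on type I error, so it should be specified at the same time.
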